### 11.0 Drug Information

#### 11.1 Camostat mesilate (Foipan®):

- 11.1.1 Background: Camostat mesilate is a serine protease inhibitor that is currently approved in Japan for pancreatitis and reflux esophagitis. Camostat mesilate acts promptly on kinin formation, fibrinolytic, coagulation and complementary systems to immediately inhibit enzyme activities and their abnormal increases. For the purposes of this study, camostat mesilate also exhibits anti-transmembrane serine protease 2 (TMPRSS2) activities. It can also void severe acute respiratory syndrome (SARS) S cleavage, inhibit cell entry and decrease viral replication.
- 11.1.2 Formulation: Camostat mesilate is available as a 100 mg film coated tablet. Each tablet also contains hydroxypropylcellulose, carmellose calcium, magnesium stearate, polyoxyethylene (105) polyoxyethylene (5) glycol, and lactose hydrate.
- 11.1.3 Preparation and storage: Camostat mesilate are packaged in bottles of 28 tablets. The recommended storage condition for camostat mesilate film coated tablets is 15° to 30°C.
- 11.1.4 Administration: Camostat mesilate tablets should be taken by mouth or via nasogastric tube four times daily on an empty stomach at least 30 minutes before each meal, 2 hours since last meal, and at bedtime. For nasogastric administration, place tablets into 55 ml of room temperature water until tablets dissolve into solution. Once tablets have dissolved, deliver the solution to

patients via nasogastric tube. If a patient is receiving continuous tube feedings, camostat dosing must be held while on continuous tube feedings.

#### 11.1.5 Pharmacokinetic information:

Absorption: After a single dose of camostat mesilate at 200 mg, Tmax values were 40 minutes with a maximum of 87.1 ng/mL

Protein binding: Protein binding to human serum was 25.8-28.2%

Metabolism: Carboxylate ester moiety of camostat mesilate is hydrolyzed to an active metabolite 4-(4-guanidinobenzoyloxy) phenylacetate, which is further hydrolyzed to 4-guanidinobenzoic acid. Camostat mesilate is mainly hydrolyzed by carboxyesterase and 4-(4-guanidinobenzoyloxy) phenylacetate by arylesterase (in vitro). Camostat mesilate and its metabolite 4-(4-guanidinobenzoyloxy) phenylacetate did not inhibit CYP1A2, CYP2C9, CYP2C19, CYP2D6 and CYP3A4 (in vitro).

Half-life elimination: Mean half-life is 100 minutes +/- 40 minutes.

Excretion: Urinary excretion rates at 5-6 hours post administration were 20% and 0.8%, respectively, and little was further recovered in urine during later periods.

#### 11.1.6 Potential Drug Interactions: Camostat mesilate did not appreciably inhibit CYP1A2, CYP2C9, CYP2C19, CYP2D6 and CYP3A4 (in vitro).

#### 11.1.7 Known potential toxicities:

Clinically significant toxicities:

- Shock or anaphylactic symptoms
- Thrombocytopenia
- Hepatic function disorder or jaundice
- Hyperkalemia

#### **Toxicities $\geq 0.1$ to $< 0.5\%$ :**

Hypersensitivity: Rash, pruritus

Gastrointestinal: Nausea, abdominal discomfort, abdominal fullness, diarrhea

Hepatic: Increased AST (GOT), ALT (GPT)

#### **Toxicities $< 0.1\%$ :**

Hematologic: Leukopenia, erythrocytopenia

Gastrointestinal: Anorexia, vomiting, dry mouth, heartburn, abdominal pain, constipation

Renal: Increased BUN, increased creatinine

Other: Edema, hypoglycemia

## Incidence unknown: Eosinophilia

11.1.8 Drug procurement: Ono Pharmaceutical Co., Ltd. will supply the drug to McKesson Specialty Pharmacy's Clinical Research Services. After the patient is registered, McKesson will receive an electronic order with the patient's treatment assignment. Upon receipt of orders, McKesson will send per patient supplies to participating institutions. The Camostat mesilate will be prepared and labeled by McKesson.

11.1.9 Temperature excursions that occur at the site should be reported by the site by contacting McKesson Speciality Pharmacy at  
[REDACTED]

## 11.2 Placebo for camostat

11.2.1 Formulation: Placebo will be available as a film coated tablet. Each tablet contains D-mannitol, low substituted hydroxypropyl cellulose, and magnesium stearate. The film coating contains hydroxypropyl methylcellulose and purified water.

11.2.2 Preparation & storage: The recommended storage condition for placebo film coated tablets is 15° to 30°C.

11.2.3 Administration: Take by mouth four times daily on an empty stomach at least 30 minutes before each meal, 2 hours since last meal, and at bedtime.

11.2.4 Drug Procurement: Ono Pharmaceutical Co., Ltd. will supply the drug to McKesson Specialty Pharmacy's Clinical Research Services. After the patient is registered, McKesson will receive an electronic order with the patient's treatment assignment. Upon receipt of orders, McKesson will send per patient supplies to participating institutions. The placebo will be prepared and labeled by McKesson.

11.2.5 Temperature excursions that occur at the site should be reported by the site by contacting McKesson Speciality Pharmacy at  
[REDACTED]

### 11.3 Remdesivir (GS-5734, Veklury®))

11.3.1 **Background:** Remdesivir is a nucleotide prodrug that is intracellularly metabolized into an analog of adenosine triphosphate that inhibits viral RNA polymerases and has broad activity against members of the filoviruses [i.e. Ebola virus, Marburg virus, CoVs (SARS-CoV, MERS-CoV) and paramxoviruses (respiratory syncytial virus, Nipha virus, and Hendra virus)].

11.3.2 **Formulation:** Remdesivir for Injection, 100 mg, is a preservative-free, white to off-white or yellow lyophilized solid containing 100 mg of remdesivir. It requires reconstitution and then further dilution prior to administration by intravenous infusion. The inactive ingredients are 3 g betadex sulfobutyl ether sodium and may include hydrochloric acid and/or sodium hydroxide for pH adjustment.

Remdesivir injection contains 100 mg/20 mL (5 mg/mL) as a sterile, preservative-free, clear, colorless to yellow solution in a single-dose clear glass vial. It requires dilution prior to administration by intravenous infusion. The inactive ingredients are 6 g betadex sulfobutyl ether sodium, Water for Injection, USP, and may include hydrochloric acid and/or sodium hydroxide for pH adjustment.

11.3.3 **Preparation and storage:** Remdesivir for Injection should be stored refrigerated at at 2°C to 8 °C [36 °F to 46 °F] prior to use.

**There are differences in the way the two formulations are prepared.  
Carefully follow the product-specific preparation instructions below.**

Remdesivir for Injection 100 mg lyophilized powder is to be reconstituted with 19 mL of Sterile Water for Injection. Immediately shake the vial for 30 seconds. Allow the contents of the vial to settle for 2 to 3 minutes. A clear, colorless to yellow solution, free of visible particulates, should result. If the contents are not completely dissolved, repeat the process of shaking for 30 seconds and allowing contents to settle for 2 to 3 minutes. Following reconstitution, each vial contains 5 mg/mL remdesivir concentrated solution with sufficient volume to allow withdraw of 20 mL (100 mg of remdesivir).

Remdesivir should be diluted into 100 to 250 mL 0.9% NaCL prior to administration by intravenous infusion. Invert 20 times to mix. Remdesivir for injection is recommended to be reconstituted and diluted within the same day as administration. The prepared infusion solution is stable for 24 hours at room temperature (20°C to 25°C [68°F to 77°F]) or 48 hours at refrigerated temperature (2°C to 8°C [36°F to 46°F]). Any unused remdesivir should be discarded.

11.3.4 Administration: Infuse intravenously over 30 minutes. The infusion time may be extended up to 120 minutes. Flush the tubing with 30 mL of 0.9% NaCL post-remdesivir infusion.

11.3.5 Pharmacokinetic information:

**Protein binding:** Remdesivir: 88% to 93.6%; GS-441524: 2%; GS-704277: 1%

**Half-life elimination:** Remdesivir: ~1 hour; GS-441524: 27 hours; GS704277:

1.3 hours

**Excretion:** Urine: Remdesivir: 10%; GS-441524: 49%; GS-704277: 2.9%;

Feces: Remdesivir: not detected; GS-441524: 0.5%; GS-704277: not detected

11.3.6 Potential Drug Interactions: Due to potential antagonism based on data from cell culture experiments, concomitant use of remdesivir with chloroquine phosphate or hydroxychloroquine sulfate is not recommended.

Drug-drug interaction trials have not been conducted in humans. Remdesivir and its metabolites are in vitro substrates and/or inhibitors of certain drug metabolizing enzymes and transporters. The clinical relevance of these assessments has not been established.

11.3.7 Known potential toxicities:

**Common known potential toxicities ≥ 10%:**

Endocrine & metabolic: Increased serum glucose

Renal: Decreased creatinine clearance

**Less common known potential toxicities 1-10%:**

Dermatologic: Skin rash

Gastrointestinal: Nausea

Hematologic & oncologic: Decreased hemoglobin, lymphocytopenia, prolonged prothrombin time

Hepatic: Increased ALT, increased AST

Hypersensitivity: Hypersensitivity reaction

Frequency not defined:

Hepatic: Increased serum alkaline phosphatase

Hypersensitivity: Anaphylaxis, angioedema

Local: Erythema at injection sites

Miscellaneous: Infusion related reaction

Postmarketing:

Cardiovascular: Bradycardia, heart failure, hypotension

Hepatic: Acute hepatic failure

11.3.8 Drug procurement: Commercial supplies. Pharmacies or clinics shall obtain supplies from normal commercial supply chain or wholesaler.

## 12.0 Treatment Evaluation Criteria

The ordinal scale used for assessment of the clinical and respiratory status on each day of the study is included below. Each day, the worst (i.e., highest ordinal) score from the previous day will be recorded, i.e., on Day 3, the highest ordinal score from Day 2 is obtained and recorded for Day 2. The scale is as defined by the WHO as follows:

Patient State	Descriptor	Score
Uninfected	No Clinical or Virological Evidence of Infection	0
Ambulatory	No Limitation of activities	1
	Limitation of activities	2
Hospitalized, Mild Disease	Hospitalized, no oxygen therapy	3
	Oxygen by mask or nasal prongs	4
Hospitalized, Severe Disease	Non-invasive ventilation or high flow oxygen	5
	Intubation and Mechanical Ventilation	6
	Ventilation + additional organ support-pressors, RRT, ECMO	7
Dead	Death	8

In addition, patients will be stratified at baseline based on the ordinal scale below. A score of 3-4 is associated with hospitalized with mild disease versus score of 5 is associated with severe disease.

The primary outcome assessment for efficacy will be evaluated based on the number of patients who are alive AND respiratory failure-free at Day 28 after study entry.

Respiratory failure at Day 28 will be defined by clinical diagnosis of respiratory failure corresponding to a score of 5-8 on the above ordinal scale at Day 28. Specifically, respiratory failure is defined by meeting any of the following criteria:

- Requiring ICU admission,
- mechanical ventilation,
- ECMO,
- non-invasive ventilation,
- or high flow oxygen devices,

## 13.0 Statistical Considerations and Methodology

### 13.1 Statistical Design

The study design will be a randomized (1:1 ratio), double-blinded, placebo-controlled phase II trial of 264 patients. Randomization will be stratified based on age (< 65 years versus  $\geq$  65 years) and disease severity at study entry (hospitalized with mild disease versus hospitalized with moderate/severe disease). The purpose of this study is to evaluate the efficacy of Camostat mesilate in addition to SOC treatment as compared to SOC treatment combined with placebo with respect to clinical status on Day 28. The proportion of patients alive AND free from respiratory failure at Day 28 will be the primary outcome.

Patients will be analyzed according to their randomization assignment. All patients meeting eligibility criteria who received at least 1 dose of study drug will be included in the analysis.

Formal interim analysis will be conducted after the first 66 patients (33 treated in the treatment arm and 33 in the control group) have completed the 28 Day assessment period. Safety analyses will be done to assess occurrence of any differences in adverse events between the treatment arms. A second interim analysis will occur after 132 patients (66 in the treatment arm and 66 in the control group) have completed the 28 Day assessment period.

### 13.2 Accrual Time and Study Duration

We expect to accrue approximately 20 patients a week across the clinical trial sites. With a total sample size of 264 and a follow-up duration of 56 days for all patients, accrual will require approximately 14 weeks with a total study duration of 22 weeks. The primary endpoint will be evaluable after 28 days of follow-up in all patients.

### 13.3 Study Endpoints

#### 13.3.1 Primary Endpoint:

The primary endpoint will be evaluated based on the number of patients who are alive AND free from respiratory failure at Day 28 after study entry divided by the number of total patients enrolled for each treatment arm. A respiratory failure event is defined in the Treatment evaluation criteria section 12.0.

#### 13.3.2 Secondary Endpoints

1. Proportion of patients alive AND free of ventilator use or ECMO at Day 28: The proportion will be evaluated based on the number of patients who are alive AND free of ventilator use or ECMO (clinical status score of 5 or less) at Day 28 after study entry divided by the number of total patients enrolled for each treatment arm.

2. Time to death: Time to death will be measured as the number of days from the date of randomization/study entry until death date. Deaths due to any cause will be considered an

event. All-cause mortality rate at 28 and 56 days after study entry will be evaluated. If the patient is lost to follow-up or withdraws from the study early, or doesn't experience a death event, they will be censored at Day 28.

**3. Time to clinical improvement:** Clinical improvement will be defined as a 2 or more point decrease on the WHO ordinal scale (see Section 12.0). Time to clinical improvement will be calculated as the number of days from study entry until the earliest date of clinical improvement as defined above. The number of patients who achieve clinical improvement by Day 14 and 28 will be evaluated. In addition, time to clinical improvement will also be assessed.

**4. Clinical status at Days 14 and 28:** Evaluation of the distribution of clinical status scores by the ordinal scale will be done at days 14 and 28.

**5. Length of Hospitalization Stay:** This will be defined as the time from randomization/study entry until the time of hospital discharge. Time in the ICU will be described in number of days spent receiving ICU care, if applicable.

**6. Duration of Mechanical ventilation / ECMO:** Ventilator / ECMO days will be defined as the number of days where the clinical status score is equal to 6 or 7 for those subjects who have a baseline score of 6-7 at study entry. Total number of days will be the sum of all reported days, regardless of whether the days occur consecutively or in disjoint intervals.

**7. Duration of non-invasive ventilation / high-flow oxygen:** Non-invasive ventilation / high-flow oxygen days will be defined as the number of days where the clinical status score is equal to 5 for those with a baseline score of 5 at study entry. Total number of days will be the sum of all reported days, regardless of whether the days occur consecutively or in disjoint intervals.

**8. Days of supplemental oxygen use:** Oxygen days will be defined as the number of days where the clinical status score is equal to 4-7 for those who have a clinical status score greater than or equal to 4 at study entry. Total number of days will be the sum of all reported days, regardless of whether the days occur consecutively or in disjoint intervals.

**9. Occurrence of adverse events related to treatment:** Adverse Events will be recorded and graded according to CTCAE version 5.0 criteria. Occurrence of grade 3 or higher adverse events and SAEs will be assessed between arms.

**10. Development of thrombosis / bleeding complications:** Incidence of arterial and venous thrombosis or bleeding complications will be described in both treatment groups.

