### 2.2 Secondary Objectives include the following:

- 2.2.1 To determine if reduction in TMPRSS2 activity via direct inhibition with Camostat mesilate combined with SOC treatment will increase the proportion of patients alive and free of ventilator use or ECMO at Day 28 as compared to SOC treatment combined with placebo.
- 2.2.2 To determine if the combination of Camostat mesilate combined with SOC treatment will result in a decreased mortality rate at 28 and 56 days as compared to SOC treatment combined with placebo.
- 2.2.3 To determine if time to clinical improvement is reduced in patients receiving SOC treatment combined with Camostat mesilate as compared to SOC treatment combined with placebo.
- 2.2.4 To determine if Camostat mesilate combined with SOC treatment is associated with overall improved clinical status at Days 14 and 28 as compared to SOC treatment combined with placebo.
- 2.2.5 To determine if Camostat mesilate combined with SOC treatment is associated with a reduced length of stay in the hospital as compared to SOC treatment combined with placebo.
- 2.2.6 To determine if Camostat mesilate combined with SOC treatment is associated with reduced duration of:
  - a) mechanical ventilation or ECMO use,
  - b) non-invasive ventilation or high-flow oxygen use, and

- c) supplemental oxygen use as compared to SOC treatment combined with placebo.
- 2.2.7 To compare the safety and toxicity profile of Camostat mesilate combined with SOC treatment as compared to SOC treatment combined with placebo.
- 2.2.8 To determine if treatment with Camostat mesilate combined with SOC treatment is associated with decreased incidence of thrombotic events and bleeding complications as compared to SOC treatment combined with placebo.

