8.5.2.3 Grade 5 AEs (Deaths)

8.5.2.3.1 Any death within 56 days after registration on the trial must be submitted as a Grade 5 AE, with a CTCAE type and attribution assigned.

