#### 13.5 Secondary Analyses

1. Proportion of patients alive AND free of ventilator use / ECMO at Day 28: The proportion will be evaluated based on the number of patients who are alive AND free of

ventilator use or ECMO at Day 28 after study entry divided by the number of total patients enrolled for each treatment arm. The proportion of patients who have this event will be analyzed similarly to the primary endpoint. Comparisons will be done by use of independent samples Z-test for proportions and a 95% confidence interval will be constructed for the difference between groups. The Cochran-Mantel-Haenszel test will be used to include stratification factors. Multivariable logistic regression models will be used to assess the influence of treatment arm on while adjusting for other factors of interest.

**2. Time to death and Mortality rate:** The Kaplan-Meier method will be used evaluate differences in the distributions of time-to-death between treatment arms. Rates of mortality at day 28 and day 56 mortality will be estimated. Patients lost to follow-up or who withdraw early will be considered censored at their last assessment date for the Day 28 rate. The stratified log-rank test will be used to compare differences in distributions of time to death based on stratification factors. Cox proportional hazards model will be used to compare treatment arms with inclusion of stratification factors or adjustment for covariates of interest.

**3. Time to clinical improvement:** Time to clinical improvement will be evaluated using Kaplan-Meier methods and Cox regression models. Rates of clinical improvement at days 14 and 28 will be estimated. Time to clinical improvement will be assessed after all patients have reached day 14 and 28; no clinical improvement at day 14 or 28 or death before day 14 or 28 will be considered as right censored. Hazard ratios with 95% confidence intervals will be calculated by the Cox proportional-hazards model. Covariates of interest will be included in regression models.

**4. Clinical status at Days 14 and 28:** The distribution of the clinical status will be summarized by arm at days 14 and 28. A proportional odds model with treatment arm and disease severity at baseline as covariates will be used to evaluate whether the odds of improvement on the ordinal scale are higher for the treatment arm as compared to control.

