#### Missing Data Considerations

All efforts will be made to minimize the occurrence of missing data. Subjects who discontinue treatment in either arm will be encouraged to remain in the study and to continue with follow-up visits for key outcomes at Day 28 and 56.

For time to event outcomes, subjects who are lost to follow-up or withdrawal from the study prior to Day 28 and prior to observing/experiencing the event will be censored at the time of their last observed assessment.

For duration of non-invasive ventilation/high-flow oxygen, ventilation/ECMO or supplemental oxygen, subjects will be considered to have the event of interest until Day

28 if they have the event of interest at their last follow-up assessment day before Day 28 in the case of lost to follow-up or patient withdrawal. Likewise, if they do not have the event of interest at their last follow-up assessment, they will be considered to not have this event through Day 28.

If the subject is discharged and no further hospitalization data are available, then the subject will be assumed to not have been readmitted to the hospital.

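### Time to death is censored at Day 28 for everyone who does not die, and no Day 56 censoring rule exists, so the planned 56-day mortality estimate is invalid if the text is followed

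*Combined protocol and SAP*

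**What the plan says.** **What is to be estimated.** Objective 2.2.2 looks for a "decreased mortality rate at 28 and 56 days". Section 13.3.2, item 2, repeats this: "All-cause mortality rate at 28 and 56 days after study entry will be evaluated". Section 13.5, item 2, names the Kaplan-Meier method, a stratified log-rank test and a Cox model, and adds: "Rates of mortality at day 28 and day 56 mortality will be estimated".

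**What is to be collected.** Section 13.2 plans "a follow-up duration of 56 days for all patients", section 10.4 schedules follow-up at Days 28 and 56, and section 8.5.2.3.1 requires: "Any death within 56 days after registration on the trial must be submitted as a Grade 5 AE".

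**How times are to be censored.** There are three statements.

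- 13.3.2, item 2: a patient who is "lost to follow-up or withdraws from the study early, or doesn't experience a death event, they will be censored at Day 28".
- 13.5, item 2: patients lost or withdrawn early "will be considered censored at their last assessment date for the Day 28 rate".
- Missing Data Considerations: patients lost or withdrawn "prior to Day 28 and prior to observing/experiencing the event will be censored at the time of their last observed assessment".

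Only the first of these deals with patients who are simply alive, and it stops their time at Day 28.

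**The concern.** A curve whose survivors all leave the risk set at Day 28 cannot support a Day 56 rate. The other two censoring statements do not fill the gap: one is limited to early losses and the Day 28 rate, the other to losses before Day 28. Patients alive at Day 56 have no Day 56 rule, and patients lost between Day 28 and Day 56 have no last-assessment rule.

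At stake is half of a named secondary objective. The log-rank and Cox analyses use the same times, so a difference in deaths after Day 28 would contribute almost nothing to them although those deaths are collected. If the statistician repairs the rule at analysis, the choice on a mortality endpoint may be made after data have been seen.

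Two smaller faults lie in the same text. For dropouts, 13.3.2 says Day 28 while 13.5 and Missing Data say last assessment. For time to clinical improvement, 13.5, item 3, right-censors deaths without naming the day.

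**Working it through.** **The plan's own figure.** Section 13.2 gives 14 weeks of accrual and 22 weeks in total. 264/20 = 13.2, rounded up to 14; 56/7 = 8; 14 + 8 = 22. This reproduces and confirms that 56-day follow-up of everyone is built into the timetable. The plan gives no mortality, event count or power for time to death, so what follows is illustration.

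**Inputs.** 132 patients per arm (13.6). Deaths by Day 28 are assumed at 11 or 15 (8.3% or 11.4%), near the 8.0% and 11.6% quoted in 1.0 Background, where no time horizon is attached. Deaths on Days 29 to 56 are assumed and varied. No losses unless stated.

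**1. Day 56 mortality in one arm.** The product-limit estimate is S(t) = ∏(1 − dᵢ/nᵢ), and mortality is 1 − S(t). With 11 early deaths, S(28) = 121/132, so Day 28 mortality is 8.3%.

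- *Correct:* survivors censored at Day 56. Mortality is (11 + late deaths)/132.
- *Reading A:* survivors censored at Day 28, late deaths kept as events. After Day 28 only patients who will die are at risk. With two late deaths the extra factors are (1 − 1/2)(1 − 1/1) = 0, so mortality is 100%.
- *Reading B:* all data cut at Day 28. Nobody is at risk afterwards, and the Day 28 value is carried forward.

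| Late deaths | Correct | Reading A | Reading B |
|---|---|---|---|
| 0 | 8.3% | 8.3% | 8.3% |
| 1 | 12/132 = 9.1% | 100% | 8.3% |
| 2 | 13/132 = 9.8% | 100% | 8.3% |
| 4 | 15/132 = 11.4% | 100% | 8.3% |
| 8 | 19/132 = 14.4% | 100% | 8.3% |

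**2. Comparison of arms.** Death times are uniform on Days 1–28 and 28–56. Entries are the mean unstratified log-rank Z over 400 runs; repeat simulations moved them by about 0.02.

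| Deaths, camostat vs control (early + late) | Correct | Reading A | Reading B |
|---|---|---|---|
| 11+2 vs 15+8 | −1.75 | −0.73 | −0.83 |
| 11+2 vs 15+4 | −1.12 | −0.77 | −0.82 |
| 11+2 vs 15+3 | −0.95 | −0.78 | −0.83 |
| 11+4 vs 15+4 | −0.75 | −0.78 | −0.83 |

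In the first row, Day 56 mortality is 13/132 = 9.8% against 23/132 = 17.4%. The median Cox hazard ratio over 60 runs is 0.55 when censored correctly, 0.78 under A and 0.72 under B.

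**3. Dropouts held alive to Day 28.** Let m be Day 28 mortality, p the proportion lost at uniform times unrelated to prognosis, and λ = −ln(1 − m)/28. Observed mortality is (1 − p)m + p[1 − (1 − e^(−28λ))/(28λ)]. For m = 11.6% and p = 10%: 28λ = 0.1233, the bracket is 1 − 0.116/0.1233 = 0.0592, and the total is 0.1044 + 0.0059 = 11.03%, which is 0.57 points low. Over p = 2% to 10% and m = 8.0% or 11.6%, the bias runs from −0.08 to −0.57 points.

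**4. Deaths in time to clinical improvement.** If deaths are carried to the Day 14 or 28 horizon as not improved, the bias is 0. If they are censored at the death date, 1 − KM estimates 1 − e^(−ah), while the true proportion improved is a/(a+b) × (1 − e^(−(a+b)h)), with a and b the improvement and death hazards and h the horizon. Assume constant hazards, a median of 11 or 15 days (the recovery medians in Background, standing in for a 2-point improvement), and 8.0% or 11.6% dying before improvement by Day 28. Then 1 − KM is 4.2 to 7.5 points too high at Day 28 and 1.6 to 3.3 at Day 14. Example: median 11 days, 11.6% deaths, Day 28, true 75.3% against 82.9%.

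**The case against.** The best defence is that the two readings are not the only ones. Section 13.5 ties its dropout rule to the Day 28 rate, so the Day 28 sentence in 13.3.2 may describe only the Day 28 analysis, with the Day 56 counterpart left out by oversight. A competent statistician would censor at Day 56, a curve falling to 100% would be noticed at once, and a crude Day 56 proportion could be formed from the reported deaths. This explains how the fault may have arisen but does not remove it. The written rule still conflicts with the objective, the repair would depart from the text, and the plan specifies no crude proportion. It does make reading A the less likely outcome; a mislabelled 28-day figure or an unplanned choice is the realistic risk.

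The objection on size has force. The drop from −1.75 needs 8 late deaths against 2, which nothing in the documents supports. With 3 or 4 against 2 the loss is modest, with equal late deaths there is none, and no case shown reaches 1.96. The simulated test is also unstratified, whereas the plan stratifies.

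Two further points stand. The clinical improvement wording can be read as censoring deaths at the horizon, like the other non-improvers, and then there is no bias. And Day 56 status is not assured for everyone: 10.3 ends follow-up on a switch to alternative therapy, and 10.4 exempts withdrawals.

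**Conclusion.** The concern holds. The censoring rule in 13.3.2 contradicts the 56-day mortality objective, and no other text supplies a Day 56 rule. Applied literally, it gives either 100% after a single late death or the Day 28 figure under a Day 56 label; in the assumed arm the correct value is 9.1% to 14.4%. The log-rank and Cox results become in effect 28-day comparisons.

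The contradiction itself rests on the text alone. Its numerical size depends on assumed late deaths: with none, the estimate is unharmed, and the loss in the arm comparison is material only when the arms differ clearly after Day 28.

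The conflict over dropouts is real but small, at most about 0.6 points on Day 28 mortality under the assumed losses. The clinical improvement point is closer to a missing detail and adds no weight here. Only secondary endpoints are touched. This should be fixed before analysis.

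**What to change.** - **13.3.2, item 2.** Delete the Day 28 censoring sentence. Write instead: *Patients not known to have died are censored at the last date known alive, administratively at Day 56; the 28- and 56-day rates are read from this one curve.* This also covers patients whose follow-up ends early under 10.3 or 10.4.
- **13.5, item 2, and Missing Data Considerations.** State the same rule, and say whether the log-rank and Cox comparisons run to Day 28 or Day 56.
- **13.5, item 3.** State either that patients who die without improvement remain in the risk set as not improved to the Day 14 or 28 horizon, or that death is a competing event analysed by cumulative incidence.

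The cost is a few sentences and a routine programming change. No new data collection is needed, since the Day 56 visit and the reporting of deaths within 56 days are already required.
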